VII- References		References by reference manager		
Evidence based committee (Reviewers)				
1. [name]		Signature		Date
2.				25-V-18
Research plan committee				
1. [name]		Signature		Date
2.				25-V-18

I. Administritive information:

1. Title:

Salivary and serum leptin levels in oral lichen planus patients : A Case-Control study.

-Research question :

Do levels of salivary and serum leptin differ between oral lichen planus patients and healthy control subjects ?

(Primary outcome is serum leptin levels)

2. Protocol registration:

The study protocol; will be registered on www.clinicaltrials.gov upon approval by the ethics committee of Faculty of Dentistry, Cairo University.

3. Protocol version:

18 July 2023, protocol number: 1

4. Funding:

Self-funding

5. Roles and responsibilities:

Investigator: [name], B.D.S 2015 Misr university for science and technology.

The principal investigator, responsible for funding and undergoing the clinical and theoretical work of the trial, collecting data, clarification and conclusions.

[name], Professor of Oral medicine and Periodontology Department, Faculty of Dentistry, Cairo University.

Role: Main supervisor

Responsibilities: initiated the study design. She will afford guidance through the clinical work, revising the theoretical part and help with the conclusions and completion of the data.

[name] [name], Professor of Medical Biochemistry and Molecular Biology, Faculty of Medicine, Cairo University.

Role: co-supervisor

Responsibilities: Assessment of leptin expression profiles in saliva and serum and interpretation of the data.

II. Introduction:

6a. Scientific background

One of the most prevalent muco-cutaneous chronic autoimmune illnesses is oral lichen planus. It has an unknown cause, however factors like systemic illness, psychological illness, dental work, and medication can increase your risk.

Leptin is a hormone that helps with weight loss and also has a role in the body's response to fasting. Leptin's effects on the immunological system, the neuroendocrine system, and development are all worth noting. Infections, endotoxins, and cytokines including tumour necrosis factor (TNF) and interleukin-1 (IL-1) all play a role in triggering this response.

6b.

One of the most prevalent muco-cutaneous chronic illnesses is oral lichen planus. There is no doubt that this is an autoimmune disorder. Despite an unknown cause, several elements, such as systemic conditions, psychogenic disorders, dental restorations, and certain medicines, should be taken into account.

Oral lesions are typically found on both sides of the mouth, most frequently in the inner buccal mucosa. It manifests in three distinct clinical presentations: reticular, atrophic, and bullous erosive.

Because of the high risk of malignant progression, the condition is classified as premalignant. Cytoid bodies and T-lymphocyte infiltration into the epithelial basal cell layer are histopathological hallmarks of the disease.

Leptin is a hormone secreted by adipocytes that stimulates autoimmune reactions. LP is linked to dyslipidemia, therefore, this research was carried out to evaluate the lipid profile and serum leptin levels in LP patients. White adipose tissue secretes the polypeptide hormone leptin.

Multiple studies have shown that elevated leptin levels correlate with increased body fat and increased body mass index. Additionally, it induces autoimmunity and participates in cellular immune response.

Leptin is thought to play a role in the pathogenesis of psoriasis due to its ability to stimulate the production of cytokines and regulate helper T cells. Beyond psoriasis, the evidence on the role of leptin in dermatological disorders is scant. It is possible that it contributes to the pathophysiology of LP.

However, there is scant information available on how much leptin is present in LP. LP is also linked to dyslipidemia. Many studies have found that LP patients have considerably different lipid profile levels compared to healthy control groups, leading researchers to believe that chronic inflammation and dyslipidemia contribute to an elevated risk of cardiovascular disease.

whether or not leptin has an effect on LP progression. The purpose of this research was to examine the relationship between blood leptin levels and LP severity in newly diagnosed individuals. We also compared leptin levels, lipid profile, and sickness duration to draw conclusions.

6c.

Assessment of salivary and serum leptin levels in oral lichen patients

III. Methods:

A) Study design and settings

7. Study design

Case-control study

The patients are divided into two groups

Case group: diseased oral lichen planus 39 patients

Control group: healthy patients 39 healthy controls

PCO:

Population: Oral Lichen Planus patients.

Control: Healthy patients.

Outcomes: Salivary and serum leptin levels.

8. Settings

All patients will be selected from the "out-patient clinic" of Oral Medicine – Oral Diagnosis and Periodontology Department; Faculty of Dentistry, Cairo University.

All controls will be selected from the "out-patient clinic" of any clinical department other than Oral Medicine; Faculty of Dentistry, Cairo University.

B) Participants

9. Eligibility criteria and selection methods

Inclusion criteria:

- Ages for both sexes fall between 30 and 70.
- Symptomatic OLP has been diagnosed clinically and verified histologically.
- Participants who sign a written consent form after being fully informed about the study

Exclusion criteria:

- Treatment with a systemic or locally administered systemic medication within the previous three months before the commencement of the research.

- Patients now taking or who have just stopped taking an NSAID (both steroid and non-steroidal) for pain or inflammation.
- Patients who have been diagnosed with a malignant tumor or tumors.
- Women who are expecting or nursing.
- Inmates, the mentally ill, the elderly, etc., all fall into this category.

rationale for choosing cases and controls for case control studies

All patients will undergo a thorough history and physical examination, and an incisional biopsy of the oral lesion will be taken for histological analysis to confirm a diagnosis of Oral Lichen Planus.

In order to make a fair comparison of salivary and serum leptin levels between cases and controls, we will select individuals who do not have any systemic or oral lesions.

10. Matching criteria and allocation ratio

Matching will be according to Age and Gender

The ratio between cases to controls is 1:1

C) Variables

11. Details about variables

Outcomes: Salivary and serum leptin levels.

Potential confounders: Age and Gender, Type of OLP

Diagnostic criteria: presence of Oral Lichen Planus form(s) (Reticular, Atrophic or Bullous-Erosive forms)

12. Data sources and management

Salivary and serum leptin levels Measurement.

-For patients in Group I, we will collect a saliva sample. Saliva and serum samples from participants in Group II (healthy controls) will be frozen at -80 degrees Celsius until ELISA testing can be performed.

-Saliva will be collected from each individual after a brief water rinsing and placed on ice in a Falcon tube of the 50 ml capacity. It will take about 5-10 minutes to gather 400 l of unstimulated entire saliva.

- Centrifugation removes insoluble components (bacteria, cellular debris, and glycoprotein aggregates) from a saliva specimen that was snap frozen and packaged in ice or liquid nitrogen immediately after collection.

-Phlebotomists should collect blood samples to ensure participants are comfortable and the sample is of sufficient quality and quantity. Clear spoken and/or written instructions, including information regarding fasting and medication avoidance as appropriate for the intended analyses, should be provided to the study participants. The gold standard for blood donations.

- Under strict hygienic conditions, a venous blood sample of 6 mL is taken from the patient after a fast of 12 hours in a plain red-capped evacuated blood collection tube. Within an hour of sample collection, they will be analysed. After the blood has coagulate, it will be centrifuged at 2000 rpm for 10 minutes to separate the serum. On the same day, regular tests will be performed, and the remaining serum will be frozen at -200 degrees Celsius for serum leptin quantification at a later date.

-The Leptin concentration in the blood will be measured using a commercially available enzyme immunoassay (ELISA) kit from DRG.

-To facilitate data collection and sample identification, we will assign a unique identifier (ID) number to each participant. The main investigator will record all participant information on a standard Excel spreadsheet. The superiors will conduct a secondary inspection.

13. Addressing potential sources of bias

Random selection of cases and controls, all personal and clinical data will be confidential, exposed only on request

D) Study size:

A power analysis was created to have enough strength to use a two-sided statistical test of the null hypothesis that there is no difference between tested groups regarding salivary and serum leptin levels. By adopting an alpha (α) level of 0.05 (5%), a beta (β) level of 0.2 (i.e. power=80%), and an effect size (d) of (0.736) calculated based on the results of a previous study.¹; the predicted total sample size (n) was found to be (62) cases (i.e. 31 cases per groups). Sample size was increased by (25%) to compensate for possible drop-out during different follow up intervals to be a total of (78) cases (i.e. 39 cases per group). Sample size calculation was performed using G*Power version 3.1.9.7²

14. Study size

Cases: 39... patients

Controls: 39.... Subjects,

E) Quantitative variables

15. Handling of quantitative variables in the analysis

Variables: Oral Lichen Planus disease, types and duration

Potential confounders: Age and Gender, personal habits

Patients will be grouped according to the disease and Outcomes. Potential confounders will be taken into consideration.

F) Statistical methods

16. Statistical methods

Categorical data will be analysed using the chi square test and given as frequency (n) and percentage (%). By examining the distribution of the data, computing the mean and median values, and applying the Kolmogorov-Smirnov and Shapiro-Wilk tests, numerical data will be examined for normality. If the data were found to be normal, the mean and standard deviation values would be reported, and an independent t-test would be used to compare the groups. The data will be given as median and range values if the assumption of normality is broken, and the Mann-Whitney U test and Friedman's test will be used to compare the groups. For all tests, the significance threshold will be set at P 0.05. With IBM® SPSS® Statistics Version 25 for Windows, statistical analysis will be carried out.

IV. Ethics and dissemination:

17a. Research ethics approval

The protocol will be proposed to the ethics committee of faculty of dentistry, Cairo University

17b. Protocol amendments

No amendments are planned; however, if any amendment was formed, it will be published as amendments to the pre-published protocol

17c. Informed consent

All participants in the study will be asked to provide an informed signed consent after full understanding of the study procedure and before allocation in the study.

17d. Confidentiality

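### Section 6b states a severity, lipid and duration purpose that the methods do not support, and Section 16 has no suitable method for the OLP types and duration listed in Section 15

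*Combined protocol and SAP*

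**What the plan says.** The combined protocol and SAP gives two accounts of what the study is for.

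- **Section 6b (background).** "The purpose of this research was to examine the relationship between blood leptin levels and LP severity in newly diagnosed individuals". The next sentence reads: "We also compared leptin levels, lipid profile, and sickness duration to draw conclusions". Earlier in the same section: "this research was carried out to evaluate the lipid profile and serum leptin levels in LP patients".
- **Section 1, Section 6c and the outcomes.** The research question is: "Do levels of salivary and serum leptin differ between oral lichen planus patients and healthy control subjects". A note beneath it reads: "Primary outcome is serum leptin levels". Section 6c gives the aim as "Assessment of salivary and serum leptin levels in oral lichen patients". The PCO statement in Section 7 and the variable list in Section 11 both say "Outcomes: Salivary and serum leptin levels".

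Two later sections bear on the analysis. Section 15, on handling variables in the analysis, lists: "Variables: Oral Lichen Planus disease, types and duration". Section 16 names the chi-square test for categorical data, the independent t-test for normal data, and the Mann-Whitney and Friedman tests for non-normal data. It names no correlation or regression method.

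**The concern.** The purpose in 6b is a within-patient-group association between leptin and severity. The research question is a comparison of patients with healthy controls. The two need different variables, possibly different eligibility rules, and different tests. If 6b stays, a report could present severity, type or duration findings as pre-stated aims although no measure or analysis was specified for them.

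The issue is not wholly confined to background text. Section 15 brings OLP types and duration into the analysis, and Section 16 does not say how either is to be related to leptin. An analyst following the plan would have to improvise for duration, and might apply Friedman's test to independent groups of patients when comparing types.

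**Working it through.** **1. What the 6b purpose needs, set against the methods.**

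| Element in 6b | What the methods provide |
|---|---|
| Severity | No score or grading. Clinical form is the nearest item; Section 11 uses it as a diagnostic criterion and a potential confounder. |
| Newly diagnosed | Section 9 requires symptomatic, histologically verified OLP and excludes treatment in the previous three months. A patient diagnosed earlier can still enter. The biopsy confirms the diagnosis but does not limit entry to new cases. |
| Lipid profile | Not an outcome and not a named assay. Section 12 mentions only unnamed routine same-day tests. |
| Duration | Listed in Section 15, with no definition, source or analysis. |

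**2. The tests in Section 16.** Duration is naturally continuous, and no listed method estimates its association with leptin. Types are independent groups of patients, with three forms named. The t-test and Mann-Whitney test compare two groups. Friedman's test takes more than two but requires related samples. No listed test therefore gives a suitable overall comparison of leptin across three types.

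**3. The plan's own sample size.** Inputs from the study-size section: d = 0.736, two-sided alpha 0.05, power 80%, 1:1 ratio.

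- Normal approximation: 2 × (1.960 + 0.842)² / 0.736² = 28.98, so 29 per group.
- Exact noncentral t: 30 per group gives power 0.800; 31 gives 0.814.
- Mann-Whitney, with relative efficiency 3/π: 32 per group.

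The stated 31 per group is reproduced to within two patients, and 31 × 1.25 = 38.75, rounded to the stated 39. This calculation concerns the case-control difference only.

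**4. What that size offers a case-only analysis.** Controls have no disease duration or type, so the usable number is 39 cases, or 31 if the planned allowance is fully used up. The smallest correlation detectable with 80% power, by Fisher's z, is:

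- Pearson: tanh(2.802 / √(n − 3)). For n = 39, tanh(2.802/6) = 0.436. For n = 31, tanh(2.802/√28) = 0.485.
- Spearman, with variance inflated by 1.06: tanh(2.802 × √1.06 / √(n − 3)). For n = 39, tanh(2.885/6) = 0.447. For n = 31, tanh(2.885/√28) = 0.497.

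The documents give no expected correlation, so the following values are assumptions (Pearson approximation; Spearman would be slightly less favourable):

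| Assumed r | Cases needed for 80% power | Power with 39 cases |
|---|---|---|
| 0.2 | 194 | 23% |
| 0.3 | 85 | 46% |
| 0.4 | 47 | 72% |
| 0.5 | 30 | 91% |

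For three equal-sized types, a one-way analysis of variance would need Cohen's f of about 0.52 with 39 cases, or 0.59 with 31. This is only a guide to a Kruskal-Wallis comparison.

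**The case against.** The strongest reply is that 6b is stray drafting. Its sentences are in the past tense within a prospective protocol and never mention saliva, and the sentence before the stated purpose is a fragment. The lipid wording also resembles the title of the first reference, an earlier case-control study. The title, research question, 6c, the outcomes and the sample-size hypothesis all concern leptin in saliva and serum. On that view the matter is editorial.

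Much of this stands, and it limits the point in four ways.

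- A reader might infer that the study cannot answer its question. The documents do not support that: the case-control comparison has outcomes, tests and a reproducible sample size.
- A reader might infer that no lipid data will exist. Blood is taken fasting and unnamed routine tests are run, so lipids are unspecified rather than shown to be absent.
- A reader might infer that no listed test could be used for types. The t-test or Mann-Whitney test could compare two types, although no such comparison is planned.
- Section 15 says nothing of severity, lipids or new diagnosis, and Section 11 treats type as a potential confounder. The spread beyond background is therefore limited to types and duration.

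The reply does not remove the conflict. Nothing marks the 6b sentences as another study's aim, and the gap between Sections 15 and 16 remains even if 6b is set aside.

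**Conclusion.** The point holds as an inconsistency between stated purposes, together with a gap in the analysis plan for types and duration. It should be corrected, but it does not threaten the main comparison.

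On size, any case-only analysis of duration would reliably detect only a fairly strong association: a Spearman correlation of about 0.45 with 39 cases, or about 0.50 with 31. The slightly smaller Pearson value of 0.44 at 39 cases is not the figure to quote, because it applies to a different coefficient and assumes no losses. These figures rest on two-sided alpha 0.05, 80% power, the Fisher z approximation and complete duration data. They describe detectability and do not predict the true association, for which the documents give no estimate.

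**What to change.** 1. **Section 6b.** Align the purpose with Sections 1 and 6c. Remove the severity, newly-diagnosed and lipid aims, or attribute them explicitly if they describe other work.
2. **Section 16, types.** Replace Friedman's test with Kruskal-Wallis for leptin across mutually exclusive OLP types. Section 11 allows a patient to have more than one form, so an assignment rule is needed, for example by predominant form.
3. **Section 16, duration.** Add Spearman correlation of leptin with duration, and define duration and how it is obtained.
4. **Status.** Label both analyses case-only and exploratory. State that 80% power at two-sided 0.05 needs a Spearman correlation of about 0.45 with 39 cases or about 0.50 with 31.

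This costs protocol wording and two simple analyses, with no added patients or assays. The downside is a narrower stated ambition and two exploratory results with low power. The alternative, keeping the 6b purpose, would cost more: a defined severity measure, a newly-diagnosed criterion, named lipid assays, an association analysis and its own sample-size justification.

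### As most naturally read, Section 9 requires controls but not cases to be free of systemic disease, so part of any leptin difference could reflect systemic health

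*Combined protocol and SAP*

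**What the plan says.** Section 7 defines the comparison group as "Control group: healthy patients 39 healthy controls". In Section 9, the paragraph on the rationale for choosing cases and controls gives fairness of the leptin comparison as the aim and says "we will select individuals who do not have any systemic or oral lesions".

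Cases qualify under Section 9 through "Symptomatic OLP has been diagnosed clinically and verified histologically", within an age range of 30 to 70 and with consent. The exclusion list includes "Treatment with a systemic or locally administered systemic medication within the previous three months before the commencement of the research", recent anti-inflammatory use, "Patients who have been diagnosed with a malignant tumor or tumors", pregnancy or nursing, and a loosely worded item on vulnerable groups. Malignancy is the only physical disease named. A history and physical examination are stated for patients, in the same sentence as the biopsy of the oral lesion.

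Section 10 says "Matching will be according to Age and Gender". Section 11 lists age, gender and OLP type as potential confounders; Section 15 lists age, gender and personal habits. Section 15 says confounders will be considered but names no method. Section 16 compares the groups with an independent t-test or, if normality fails, rank-based tests.

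On background, Section 6a says of OLP that "factors like systemic illness, psychological illness, dental work, and medication can increase your risk". Section 6b links lichen planus to dyslipidemia and says "Multiple studies have shown that elevated leptin levels correlate with increased body fat and increased body mass index".

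**The concern.** A case-control comparison of a biomarker is interpretable when the groups differ in the disease and otherwise meet the same entry conditions. Here a health condition appears to be imposed on one side only. By the protocol's own account, systemic illness goes with OLP, so the condition removes from controls something expected to be more common in cases. If that illness also shifts leptin, the serum difference (the primary outcome) mixes an OLP contribution with a systemic-health contribution, and the planned analysis cannot separate them. Who was recruited cannot be changed afterwards, and neither systemic disease nor body mass index is listed as a covariate that would allow later adjustment.

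**Working it through.** **Step 1: compare the entry rules.**

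| Condition | Case | Control |
|---|---|---|
| Malignancy | excluded | excluded |
| Systemic disease treated with drugs in the last three months | excluded by the medication rule | excluded by the medication rule |
| Recognised systemic disease, no drug treatment | admissible | not admissible, if healthy and free of systemic lesions means free of systemic disease |
| Undeclared or undiagnosed disease | can enter | can enter |

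Only the third row differs between the groups.

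**Step 2: look for a later correction.** Matching covers age and gender. Neither confounder list names systemic disease or body mass index, no adjustment method is given, and the tests are unadjusted. Section 13 mentions random selection, but that does not equalise groups drawn under different eligibility rules.

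**Step 3: reproduce the plan's sample size, for scale.** Inputs from part D (Study size): d = 0.736, two-sided alpha 0.05, power 80%, ratio 1:1. The noncentral t-distribution gives 30 per group (power 80.0%). The stated 31 per group gives 81.4% and 39 per group gives 89.4%. The stated total of 78 is 62 × 1.25 = 77.5, rounded up. The stated size is reproduced to within one per group, and this point does not depend on it.

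**Step 4: illustrate the size of the bias.** The documents give neither the share of cases affected nor the effect on leptin, so both are assumptions. Let a share p of cases have a condition that raises leptin by k SD, with no affected controls, no OLP effect and normal data with unit SD within strata.

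- Mean difference = p × k.
- Case variance = 1 + p(1 − p)k²; control variance = 1.
- Spurious d = p × k / √[(2 + p(1 − p)k²)/2].
- The chance of p < 0.05 comes from the two-sided noncentral t with 76 degrees of freedom and noncentrality d × √(39/2).

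Worked example, p = 0.4 and k = 0.8: the mean difference is 0.32; the variance term is 0.4 × 0.6 × 0.64 = 0.1536; d = 0.32/√(2.1536/2) = 0.32/1.038 = 0.31; noncentrality = 0.308 × 4.416 = 1.36; the rejection rate is 27.0%.

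| Share of cases (p) | Shift (k) | Spurious d | False-positive rate |
|---|---|---|---|
| 5% | 0.5 SD | 0.025 | 5.1% |
| 10% | 0.8 SD | 0.08 | 6.4% |
| 20% | 0.5 SD | 0.10 | 7.2% |
| 20% | 0.8 SD | 0.16 | 10.4% |
| 40% | 0.5 SD | 0.20 | 13.8% |
| 40% | 0.8 SD | 0.31 | 27.0% |

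A simulation of 40,000 trials per setting agrees where the settings coincide: 7.0% for p = 0.2, k = 0.5 and 14.0% for p = 0.4, k = 0.5. Against the planned d of 0.736, the spurious d runs from about 3% (0.025/0.736) to 42% (0.31/0.736).

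**The case against.** The strongest reply is that the rule is being read more firmly than it is written. The sentence refers to lesions, not disease, and to individuals, not controls. Only its oral part is impossible for cases; its systemic part could be meant for both groups. That stands: the control-only reading is an inference, though a natural one given that controls are called healthy and the case criteria contain no matching item. If both groups were meant, the criteria still need to say so.

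Second, the medication rule already removes drug-treated disease, and the share of affected cases left may be small. At 5-10% the false-positive rate is 5.1-6.4%, close to nominal. This also stands, and is why the range starts there.

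Third, the chain from systemic illness to leptin is incomplete in the documents. The leptin driver they state clearly is body fat and body mass index, and no rule removes high body mass index from controls. The protocol does not say that dyslipidemia raises leptin, and what infections and cytokines trigger is unclear in Section 6a. Dyslipidemia and chronic inflammation might also be part of the lichen planus picture rather than a separate confounder. So the bias is conditional on the conditions concerned raising leptin.

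Fourth, comparison with healthy subjects is the stated research question. As description, that comparison survives; what is limited is attributing a difference to OLP itself.

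Two stronger readings are tempting. A reader might infer that all untreated or undeclared disease sits in cases only. But undeclared disease can also get past control selection, since no screening of controls is described. A reader might also infer that a significant result could not be attributed to OLP at all. The figures do not support that: even the top of the range explains less than half of the planned effect.

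**Conclusion.** The point holds as an unequal or, at best, unclear eligibility rule. Recognised systemic disease without drug treatment may enter the case group and not the control group, and nothing in the matching, the confounder lists or the tests corrects it. Its effect on the primary serum comparison lies between negligible and material (a false-positive rate of 5.1-27%) and cannot be narrowed from the documents. The range rests on the assumed shares and shifts, on no controls being affected, on no true OLP effect and on a t-test of normal data. An inflated difference requires that the conditions raise leptin and that any true OLP effect runs the same way. The change is worth making before recruitment because it is cheap. The documents do not show that the comparison is invalid.

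**What to change.** In Section 9, state explicitly that the same systemic-disease criterion applies to cases and controls, replace the reference to systemic lesions with the conditions meant, and apply to controls the history and examination now stated only for patients.

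If the sponsor prefers not to restrict cases, record systemic conditions in both groups and add to Section 16 a sensitivity analysis limited to participants without them. This is an alternative, not an addition: once both groups are restricted, that analysis would repeat the primary one.

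The cost is a short protocol amendment, a somewhat smaller pool of eligible cases, a conclusion limited to OLP without recognised systemic disease, and a brief screen for controls. Neither option deals with body mass index, which needs to be measured in its own right.

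### BMI is not recorded, matched on or adjusted for, although the protocol itself says leptin rises with body fat and BMI

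*Combined protocol and SAP*

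**What the plan says.** The research question in Section 1 is "Do levels of salivary and serum leptin differ between oral lichen planus patients and healthy control subjects", with serum leptin as the primary outcome. The background in Section 6b states: "Multiple studies have shown that elevated leptin levels correlate with increased body fat and increased body mass index". This is the only mention of BMI in the text available. The same section says of leptin and lichen planus (LP): "It is possible that it contributes to the pathophysiology of LP".

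The methods do not carry the BMI statement forward:

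- **Matching (Section 10):** "Matching will be according to Age and Gender", at a 1:1 ratio.
- **Confounders (Section 11):** "Potential confounders: Age and Gender, Type of OLP".
- **Confounders (Section 15):** "Potential confounders: Age and Gender, personal habits", followed by "Potential confounders will be taken into consideration". No method is given.
- **Data collection (Sections 9 and 12):** a history and physical examination, described in connection with confirming the OLP diagnosis, and a general instruction to enter participant information in a spreadsheet. Height, weight and BMI are not named, and eligibility sets no weight limit.
- **Analysis (Section 16):** chi-square, independent t-test, Mann-Whitney and Friedman tests.
- **Source of participants (Sections 8 and 13):** cases come from the Oral Medicine outpatient clinic and controls from other departments' clinics. Both are described as randomly selected.

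**The concern.** A variable confounds this comparison if it is related to leptin and its distribution differs between the case and control sources. The protocol itself supplies the first condition. For the second, cases and controls are drawn from different clinics. Random selection within each clinic would not remove a difference between the clinics, and matching on age and gender would not necessarily do so.

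The stated question, whether levels differ, is still answered by the unadjusted test, and chance imbalance in BMI is already covered by its 5% error rate. What is at stake is interpretation. The background raises leptin as a possible contributor to LP. If cases are systematically heavier, adiposity alone could produce a leptin difference that is then attributed to OLP. If cases are leaner, a real OLP-related rise could be partly hidden. Without height and weight, neither possibility could be examined afterwards.

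**Working it through.** **1. The plan's own figure.** Inputs from part D (Study size): two-sided alpha 0.05, power 80%, "an effect size (d) of (0.736) calculated based on the results of a previous study", giving 31 per group (62 in total), raised by 25% to 39 per group (78).

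Power of the two-sample t-test comes from the noncentral t distribution with df = 2n − 2 and noncentrality d × √(n/2):

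- n = 30: 80.0%
- n = 31: 0.736 × √15.5 = 2.90, power 81.4%
- n = 39: power 89.4%

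The stated 62 is therefore within two participants of the exact answer (60), and 62 × 1.25 = 77.5, rounded up to 78. The sample size is not the problem here.

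**2. Assumptions.** The documents give neither a leptin–BMI correlation nor a BMI gap. I assume a within-group correlation r of 0.4 to 0.6 and a systematic gap g of 0.1, 0.25 or 0.5 SD. The leptin difference produced by BMI alone, in within-group SD units, is r × g.

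**3. No OLP effect, cases and controls differ in BMI.** Put d = r × g into the formula above. For r = 0.5, g = 0.5 and n = 39, d = 0.25, the noncentrality is 0.25 × √19.5 = 1.10, and the probability of a significant result is 19.3%. Results for r = 0.4 / 0.5 / 0.6:

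| BMI gap | 31 per group | 39 per group |
|---|---|---|
| 0.1 SD | 5.3 / 5.4 / 5.6% | 5.4 / 5.6 / 5.8% |
| 0.25 SD | 6.7 / 7.7 / 9.0% | 7.2 / 8.5 / 10.0% |
| 0.5 SD | 12.1 / 16.2 / 21.3% | 14.1 / 19.3 / 25.8% |

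These are errors only if the difference is attributed to OLP.

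**4. OLP raises leptin by 0.736 SD, but cases are leaner.** Put d = 0.736 − r × g. Unadjusted power for r = 0.4 / 0.5 / 0.6:

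| BMI gap | 31 per group | 39 per group |
|---|---|---|
| none | 81.4% | 89.4% |
| 0.25 SD | 69.3 / 65.8 / 62.2% | 79.2 / 75.9 / 72.4% |
| 0.5 SD | 54.6 / 46.9 / 39.3% | 64.7 / 56.3 / 47.7% |

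**5. Power of a BMI-adjusted comparison.** The noncentrality is [d_direct / √(1 − r²)] × √(n/2) / √(1 + (g²/4) × 2n/(2n − 2)), with df = 2n − 3. Adding age and sex, if they explain nothing further, changes power by at most 0.1 point. The result depends on what 0.736 represents, which the plan does not say.

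- *0.736 is independent of BMI.* With r = 0.5 and 31 per group, power is 90.8% with no gap and 89.1% with a 0.5 SD gap.
- *0.736 already includes a BMI gap*, so d_direct = 0.736 − r × g. For r = 0.5 and g = 0.5, d_direct = 0.486. At 31 per group the noncentrality is 0.561 × 3.937 / 1.032 = 2.14 and power is 55.8%; at 39 per group it is 66.0%. Over a wider range of r = 0.3–0.7, a 0.5 SD gap gives 53–64% (31 per group) and 63–74% (39 per group); a 0.25 SD gap gives 76–86% and 85–93%.

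A simulation of this second case (20,000 runs per setting) agreed to within about one percentage point. With no OLP effect, r = 0.5 and a 0.5 SD gap, the BMI-adjusted test was significant in 5.2% (31 per group) and 4.9% (39 per group) of runs, so adjustment restores the nominal error rate.

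**The case against.** The strongest reply is that the plan asks only whether levels differ, and its test answers that. The causal reading rests mainly on one hedged background sentence, and no methods section commits to attributing a difference to OLP independently of adiposity. This stands: the defect limits interpretation and does not invalidate the test.

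Nor do the documents link OLP to BMI. The link they state is to dyslipidemia. Both groups attend outpatient clinics of the same faculty and are matched on age and gender. This also stands: a gap is possible but not shown, and a 0.1 SD gap would be trivial.

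The wording on examination, participant information and confounders could be read as leaving room for BMI. This is weak. None of it names BMI or a method, and the examination is described with the OLP diagnosis, so it does not clearly cover controls.

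Finally, adjustment is not automatically right. Section 6a says leptin helps with weight loss, so BMI may be partly a consequence of leptin, and adjusting for it could remove part of the difference of interest. That is a reason to report both estimates, not a reason to leave BMI unmeasured.

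**Conclusion.** The concern holds in its conditional form and should be fixed. That BMI is missing from the matching, the confounder lists, the named data and the analysis is clear from the text. The consequence depends on a systematic BMI gap that the documents neither show nor rule out.

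Under the assumed correlations, the effect ranges from negligible at a 0.1 SD gap to material at 0.5 SD. At the larger gap, roughly 12–26% of studies with no OLP effect would be significant through BMI alone, across 31 and 39 per group. With leaner cases, power for the planned effect would fall to 39–65%. These figures illustrate scale and do not predict bias. The case for acting rests on the protocol's own statement about leptin and BMI, the low cost of measuring it, and the fact that it cannot be recovered reliably after sampling.

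**What to change.** Before sampling starts:

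1. Record height and weight of every case and every control at the sampling visit, stating explicitly in Section 12 that this includes controls.
2. Add BMI to the confounder lists in Sections 11 and 15.
3. In Section 16, pre-specify a linear regression of serum leptin (log scale if skewed) on group, BMI, age and sex, with the same model for salivary leptin. Report it beside the planned unadjusted comparison, which stays as it is.
4. Report BMI by group.
5. Do not attribute a difference specifically to OLP without presenting the BMI-adjusted estimate. Where the two results disagree, say so and treat neither as decisive.
6. State that the planned 80% power applies to the unadjusted comparison.

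The cost is two brief, non-invasive measurements on 78 people and a short amendment, for which Section 17b already provides. The adjusted estimate may have less than 80% power: about 56% at 31 and 66% at 39 per group if 0.736 already contains the effect of a 0.5 SD BMI gap (r = 0.5).
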